## 7. ENDPOINTS AND COVARIATES

### 7.1. Efficacy Endpoint(s)

*Objective tumor response, as assessed using the Response Evaluation Criteria in Solid Tumor (RECIST) version 1.1 by calculating the Overall Response Rate (ORR), Progression Free Survival (PFS), and Overall Survival (OS).*

All efficacy endpoints are secondary in this study, which include objective tumor response, progression-free survival (PFS), and overall survival (OS) in the expansion cohort. The above efficacy endpoints are derived based on the disease response per investigator evaluation on the CRF pages, which is the primary method of documentation of disease.

- **Overall Response (OR)** – is defined as confirmed complete response (CR) or confirmed partial response (PR) according to RECIST 1.1 ([Appendix 2](#)). Confirmed responses are those that persist on repeat imaging study at least 4 weeks after the initial documentation of response. Patients who do not have on-study radiographic tumor re-evaluation, who receive anti-tumor treatment other than the study medication prior to reaching a CR or PR, or who die, progress, or drop out for any reason prior to reaching a CR or PR will not

be counted as responders in the assessment of OR. Clinical benefit response (CBR) is defined as a CR, PR or SD  $\geq 6$  cycles.

- **Progression Free Survival (PFS)** - is defined as the time from Cycle 1 Day 1 (C1D1) to first documentation of disease progression or to death due to any cause, whichever occurs first. Subjects last known to be 1) alive 2) on treatment or within the post-treatment follow-up period and 3) progression-free, are censored at the date of the last disease assessment that verified lack of disease progression. Subjects who start new anti-cancer treatment prior to the end of post-treatment follow-up period and have adequate baseline and on-treatment objective disease assessments without evidence of progressive disease are censored at the date of the last objective disease assessment. Subjects with inadequate baseline or no on-study disease assessments are censored at C1D1 unless death occurred prior to the first planned assessment (in which case the death is an event). Subjects with at least one on-study disease assessment who discontinue treatment without disease progression and without death within 28 days of discontinuation are censored at the date of the last objective disease assessment that verified lack of disease progression (if progression or death is within 28 days of discontinuation the progression or death is an event). Subjects with documentation of progression or death after an unacceptably long interval ( $>16$  weeks) since the previous disease assessment will be censored at the time of the previous assessment.

PFS (days) = [progression/death date – C1D1 + 1].

- **Overall survival (OS)** is defined as the time from initial dose until death from any cause, and is measured in the intent-to-treat population.

More details of censoring are provided in [Appendix 3](#).

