2.1.2. Dose Expansion (Part 2) Objectives

Primary Objectives

- To confirm safety and tolerability and explore preliminary evidence of anti-tumor activity of PF-06650808 at the RP2D in patients with triple negative breast cancer.

Secondary Objectives

- To evaluate the overall safety profile at the R2PD.
- To characterize the single and multiple dose pharmacokinetics of ADC (PF-06650808), total antibody (PF-06460005) and unconjugated payload (PF-06380101).
- To evaluate the immunogenicity of PF-06650808.

CCI

- CCI

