2.2. Endpoints

Primary Endpoint (Part 1)

- First cycle Dose Limiting Toxicities (DLTs) in order to determine the MTD and RP2D.

Primary Endpoint (Part 2)

- Response rate (RR) as determined by the Response Evaluation Criteria in Solid Tumor (RECIST) version 1.1 criteria.

Secondary Endpoints

- Adverse Events (AEs) as characterized by type, frequency, severity (as graded by NCI CTCAE v.4.03), timing, seriousness and relationship to study treatment.
- Laboratory abnormalities as characterized by type, frequency, severity (as graded by NCI CTCAE v. 4.03) and timing.
- Vital Signs.
- Systemic pharmacokinetic (PK) exposure of ADC (PF-06650808), total antibody (PF-06460005) and unconjugated payload (PF-06380101) will be determined with validated methods. Standard noncompartmental PK parameters will be determined from the respective concentration-time data.
- Immunogenicity of ADC (PF-06650808); Human serum ADA (anti-PF-06650808 antibody) samples will be analyzed for the presence or absence of anti-PF-06650808 antibodies, following a tiered approach using screening, confirmation and titer/quantitation.
- Objective tumor response, as assessed using the Response Evaluation Criteria in Solid Tumor (RECIST) version 1.1 by calculating the Overall Response Rate (ORR), Progression Free Survival (PFS), and Overall Survival (OS) – Part 2 only.

CCI [REDACTED]

- CCI [REDACTED]
- CCI [REDACTED]
- CCI [REDACTED].
- CCI [REDACTED]

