Like all Bayesian methods, mCRM may be sensitive to prior information placed on the model parameter β at the beginning of the trial. However, as the trial progresses and DLT data accumulates, it eventually overrules the prior information and the latter becomes less important. Furthermore, a non-informative prior distribution is used for β in this study. Although simulation was performed assuming a maximum dose of 6.4 mg/kg, actual doses may be limited at this or a lower dose level until additional information is obtained to support a higher dose exposure.

Due to binomial data variability in small samples, DLTs may be observed in a first cohort at 0.2 mg/kg simply by chance even when the true $\text{Pr}(\text{DLT} \text{ at } 0.2 \text{ mg/kg})$ is fairly low. This could result in the estimated posterior DLT rate at 0.2 mg/kg (and all higher doses) to exceed the targeted 25% very early in the trial, triggering an early stop when very few patients (2-4) have been treated. To prevent stopping the trial prematurely for futility in such cases, a step-down option with dose 0.14 mg/kg (a 30% reduction from starting dose) is added to the dose grid. This dose will be explored only if a high DLT rate occurs in the first cohort assigned to 0.2 mg/kg, ie, it will not be used as a starting dose.

9.2.2. Part 2

Part 2 of this study is intended to confirm the safety and tolerability of the dose selected in Part 1 while assessing the antitumor activity of PF-06650808 in patients with TNBC. The DLT rate and its 95% confidence interval at the selected dose may be estimated.

Analyses may be performed on data from both Part 1 and Part 2 to explore the relationships between PK parameters, safety endpoints, and efficacy endpoints.

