### ***Dose Expansion (Part 2) Objectives***

*Primary Objective:*

- *To confirm safety and tolerability and explore preliminary evidence of anti-tumoractivity of PF-06650808 at the RP2D in patients with TNBC.*

*Secondary Objectives:*

- *To evaluate the overall safety profile at the R2PD.*
- *To characterize the single and multiple dose pharmacokinetics of ADC (PF-06650808), total antibody (PF-06460005) and unconjugated payload (PF-06380101).*
- *To evaluate the immunogenicity of PF-06650808.*

CC1 [REDACTED] :

- CC1 [REDACTED]

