## 7.2. Safety Endpoints

### 7.2.1. DLT Definition

Dose limiting toxicity (DLT) is the primary endpoint of this study. Severity of adverse events will be graded according to CTCAE version 4.03. For the purpose of dose escalation, any of the following adverse events which are not considered related to disease progression occurring in the first cycle of treatment (21 days) will be classified as DLTs:

- *Hematologic:*
  - *Grade 4 neutropenia lasting  $>7$  days.*
  - *Febrile neutropenia (defined as neutropenia  $\geq$  Grade 3 and a single body temperature  $>38.3^{\circ}\text{C}$  or a sustained temperature of  $\geq 38^{\circ}\text{C}$  for more than one hour).*
  - *Grade  $\geq 3$  neutropenia with infection.*
  - *Thrombocytopenia (of any grade) associated with clinically significant or life-threatening bleeding.*

- *Grade 4 thrombocytopenia  $\geq 72$  hours or platelets  $\leq 10,000/mm^3$  regardless of duration.*
- *Non-hematologic:*
  - *Grade  $\geq 3$  toxicities, except those that have not been maximally treated (eg, nausea, vomiting, diarrhea).*
  - *Delay by more than 2 weeks in receiving the next scheduled cycle due to persisting toxicities not attributable to disease progression.*

*In addition, clinically important or persistent toxicities that are not included in the above criteria may be considered a DLT following review by the sponsor and the investigators.*

*Grade  $\geq 3$  cytokine release syndrome, infusion reaction, and allergic reaction will not be considered as DLTs but may be a reason for study discontinuation and should be reviewed with the sponsor.*

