### **9.2. Statistical Analyses**

#### **9.2.1. Primary Analysis**

Dose Limiting Toxicity (DLT) is the primary endpoint of the dose escalation component of the study, which will be summarized by dose level using the Safety Analysis Set for patients in the dose escalation portion of the study. A listing of the DLTs will also be provided.

If necessary, a summary and listing of the DLT may be provided using the Per Protocol Analysis Set for patients in the MTD expansion portion of the study.

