#### **9.2.2. Secondary Analyses**

##### **9.2.2.1. Efficacy Analysis**

In this Phase 1 study efficacy is a secondary objective. Note that the efficacy analysis is to be conducted for patients in the MTD expansion cohorts who are in the Safety Analysis Set and have baseline disease assessment and at least one post-baseline disease assessment. In the event that a large number of patients in the escalation portion of the study have the same malignancy, the efficacy analysis may be conducted.

Summary tables of best Overall Response Rate, Progression Free Survival, and Overall Survival will be provided overall and by malignancy if necessary. Efficacy listings will be provided that include best response, first CR/PR date, last date with CR or PR, most recent date without progression, progression date, death date, date of first response and last tumor assessment date, etc.

A response rate overall for Part 1 dose escalation and response rates by low, medium, and high dose groups may be presented.

The following table provides an overview of the efficacy analysis.

Endpoint	Analysis Set	Statistical Method	Model/ Covariates/ Strata*	Missing Data	Interpretation
Overall response	Per Protocol, expansion cohorts, etc.	Exact CI	By dose range/ malignancy	Censored per Section 11.3	Secondary Analysis
Progression Free Survival (PFS)	Per Protocol, expansion cohorts	Kaplan-Meier	By malignancy	Censored per Section 11.3	Secondary Analysis
Time to Progression (TTP)	Per Protocol, expansion cohorts	Kaplan-Meier	By malignancy	Censored per Section 11.3	Secondary Analysis
Duration of Response (DR)	Per Protocol, expansion cohorts	Kaplan-Meier	By malignancy	Censored per Section 11.3	Secondary Analysis

\* If patients in dose escalation phase are included.

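### Response rate is the Part 2 primary endpoint in the protocol but secondary in the SAP, so no Part 2 analysis is designated primary

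*SAP*

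**What the plan says.** The protocol gives Part 2 a two-limbed primary objective (Protocol 2.1.2): "To confirm safety and tolerability and explore preliminary evidence of anti-tumor activity of PF-06650808 at the RP2D in patients with triple negative breast cancer". Its primary endpoint for Part 2, in the synopsis and in section 2.2, is "Response rate (RR) as determined by the Response Evaluation Criteria in Solid Tumor (RECIST) version 1.1 criteria". The secondary list in section 2.2 then includes overall response rate again, marked as applying to Part 2 only.

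SAP 2.3 repeats the two-limbed objective and still labels it primary. SAP 7.1 then states: "All efficacy endpoints are secondary in this study, which include objective tumor response, progression-free survival (PFS), and overall survival (OS) in the expansion cohort". SAP 9.2.2.1 adds: "In this Phase 1 study efficacy is a secondary objective", and its overview table marks overall response as a secondary analysis. SAP 7.2.1 says: "Dose limiting toxicity (DLT) is the primary endpoint of this study".

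SAP 9.2.1, the primary analysis section, commits to a DLT summary by dose level for the escalation part. For the expansion part it says only: "If necessary, a summary and listing of the DLT may be provided using the Per Protocol Analysis Set". Protocol 9.2.2 is equally permissive, and SAP 4.2.2 repeats it: "The DLT rate and its 95% confidence interval at the selected dose may be estimated".

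**The concern.** The two governing documents rank the same endpoint differently for the same patients, and nothing reconciles them. The SAP presents itself as a supplement to the protocol, records no change to the endpoint hierarchy and gives no reason for one.

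In a cohort with no comparator and no test, the pre-specified estimate is what the study delivers. Protocol 3.1 says Part 2 is meant to provide an estimate of the likely response rate. Treatment is open label, and SAP 7.1 takes response from the investigator's evaluation. If the SAP does not say which Part 2 result is primary, which patients it covers, or whether the DLT rate is shown, those choices can be made after the data are known. A report written strictly to the SAP would also present the protocol's primary outcome as a secondary one.

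**Working it through.** The plan contains no power or error-rate calculation to reproduce. SAP 4.1 and 9.1 exclude hypothesis testing, and SAP 5 bases the Part 2 size on clinical considerations. The stated total does reproduce: Part 1 maximum 35 + Part 2 20 = 55.

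**Step 1. The role given to response rate in Part 2.**

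| Place | Role |
|---|---|
| Protocol synopsis and 2.2, primary endpoint | Primary |
| Protocol 2.2, secondary list (as ORR) | Secondary |
| Protocol 9.6.1, analysis of primary endpoint | Mentioned descriptively; only escalation DLTs are called primary |
| SAP 2.3, Part 2 objectives | Anti-tumour activity is part of the primary objective |
| SAP 7.1 and 9.2.2.1 | Secondary |
| SAP 9.2.1, primary analysis | Absent |

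The conflict is primary against secondary. It lies mainly between the documents, but each also contains part of it.

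**Step 2. What is firm and what is optional for Part 2.**

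- Response: firm. SAP 9.2.2.1 commits to summary tables for the expansion cohort, and SAP 9.1 to exact two-sided 95% intervals for binary endpoints.
- Adverse events and laboratory abnormalities: firm. SAP 9.2.3 summarises both on the Safety Analysis Set, which holds every treated patient and so includes Part 2.
- DLT rate and its interval: optional in Protocol 9.2.2, SAP 4.2.2 and SAP 9.2.1.

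None of these is designated primary for Part 2.

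**Step 3. The response denominator.** The documents give four rules:

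- Protocol 9.4.1: dosed, with a baseline tumour assessment and measurable disease.
- SAP 7.1: patients without on-study radiographic re-evaluation are not responders, which implies that they stay in the denominator.
- SAP 9.2.2.1, text: Safety Analysis Set patients with both a baseline and a post-baseline assessment, which removes those same patients.
- SAP 9.2.2.1, table: the Per Protocol set in the expansion cohorts, with an open-ended addition.

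To see the effect, use the exact (Clopper-Pearson) interval for x responders in n patients: lower limit = 2.5% quantile of Beta(x, n − x + 1); upper limit = 97.5% quantile of Beta(x + 1, n − x). Assume, for illustration only, 20 treated patients, 4 responders and 3 patients without a post-baseline scan.

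- Kept as non-responders: 4/20 = 20.0% (5.7 to 43.7).
- Excluded: 4/(20 − 3) = 4/17 = 23.5% (6.8 to 49.9).

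The estimate moves by 23.5 − 20.0 = 3.5 percentage points and the upper limit by 49.9 − 43.7 = 6.2 points, with no change in the data.

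**Step 4. What a designated primary estimate would deliver.** With n = 20 and illustrative responder counts:

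| Responders | Rate | Exact 95% interval |
|---|---|---|
| 0 | 0% | 0 to 16.8 |
| 2 | 10% | 1.2 to 31.7 |
| 4 | 20% | 5.7 to 43.7 |
| 6 | 30% | 11.9 to 54.3 |

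The designation changes no sample size. The intervals are wide, as expected for an exploratory cohort.

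**Step 5. What counts as a confirmed response.** The Schedule of Activities and Protocol 7.4 require the confirming assessment within 4 weeks of first meeting the criteria. Protocol 9.4.1 and SAP 7.1 require it at least 4 weeks after. Taken together these leave only the 4-week point itself, so the numerator is not cleanly defined either.

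**The case against.** The strongest reply is that little depends on the label. The study is exploratory, with no hypothesis, alpha or decision rule tied to Part 2. The response analysis is committed and defined in some detail, and tolerability is covered by firm adverse event and laboratory summaries. Because the SAP supplements the protocol, one can argue that the protocol's endpoint governs anyway.

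Much of this stands, and it rules out three stronger readings that a reader might infer.

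- That Part 2 could end with no analysis of response or tolerability. SAP 9.1, 9.2.2.1 and 9.2.3 commit to both; only the DLT rate is optional.
- That the SAP makes DLT a rival primary endpoint for Part 2. The sentence in SAP 7.2.1 is broad, but SAP 9.2.1 limits primary DLT to dose escalation, as do Protocol 2.2 and 9.6.1. No section names DLT as the Part 2 primary endpoint.
- That a false-positive rate is inflated. Without a test there is none to inflate.

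It is also fair to say that the two documents agree in leaving the Part 2 DLT rate optional. Making it firm is a recommendation that follows from the safety limb of the objective, not the repair of a contradiction.

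The reply does not remove the conflict itself. The protocol chose a Part 2 primary endpoint, and the SAP expressly demotes it. Treating the protocol as governing would restore the label but would settle neither the population nor the confirmation rule.

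**Conclusion.** The concern holds in this form: Part 2 lacks an analysis designated primary, although the analyses themselves are mostly planned. It affects the primary result for all of the approximately 20 expansion patients. The damage is to pre-specification and to reporting of the primary outcome, not to any error rate or sample size.

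The unsettled denominator is the part with a numerical effect: 3.5 percentage points on the estimate in the illustration. That figure rests on the assumed 4 responders and 3 unscanned patients; with no unscanned patients, the SAP 9.2.2.1 text would not lower the denominator on that account. The rest of the conclusion rests on the wording of the two documents and needs no assumption about the data. The conflict should be resolved before the final analysis.

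**What to change.** **In the SAP**

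- In 7.1 and 9.2.1, designate confirmed RECIST 1.1 response rate as the Part 2 primary endpoint, reported with the exact two-sided 95% interval of SAP 9.1.
- Fix one denominator: all treated Part 2 patients with a baseline assessment and measurable disease (Protocol 9.4.1), counting those without a post-baseline scan as non-responders, as SAP 7.1 already does. This replaces the two populations in SAP 9.2.2.1 for this endpoint.
- Narrow the statements in 7.1 and 9.2.2.1 that efficacy is secondary so that they no longer cover Part 2 response rate.
- Limit the statement in 7.2.1 that DLT is the primary endpoint to Part 1, matching 9.2.1.
- In 4.2.2 and 9.2.1, make the Part 2 DLT rate with its 95% interval a committed summary for the safety limb, and state its analysis set.

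**In the protocol**

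- Remove the duplicate ORR from the secondary list in 2.2.
- Make the DLT sentence in 9.2.2 match the SAP.

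**In both documents**

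- Reconcile the confirmation timing across the Schedule of Activities, Protocol 7.4, Protocol 9.4.1 and SAP 7.1.

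If the sponsor does intend response to be secondary, the alternative is to amend the protocol endpoint and give the reason.

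The cost is a SAP revision and a short protocol clarification; the designations and the denominator need no new patients, visits or data. The sponsor loses some discretion over what is shown for Part 2. The response rate may be slightly lower on the fixed denominator, because patients without a post-baseline scan stay in it.

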## 7.2. Safety Endpoints

### 7.2.1. DLT Definition

Dose limiting toxicity (DLT) is the primary endpoint of this study. Severity of adverse events will be graded according to CTCAE version 4.03. For the purpose of dose escalation, any of the following adverse events which are not considered related to disease progression occurring in the first cycle of treatment (21 days) will be classified as DLTs:

- *Hematologic:*
  - *Grade 4 neutropenia lasting  $>7$  days.*
  - *Febrile neutropenia (defined as neutropenia  $\geq$  Grade 3 and a single body temperature  $>38.3^{\circ}\text{C}$  or a sustained temperature of  $\geq 38^{\circ}\text{C}$  for more than one hour).*
  - *Grade  $\geq 3$  neutropenia with infection.*
  - *Thrombocytopenia (of any grade) associated with clinically significant or life-threatening bleeding.*

- *Grade 4 thrombocytopenia  $\geq 72$  hours or platelets  $\leq 10,000/mm^3$  regardless of duration.*
- *Non-hematologic:*
  - *Grade  $\geq 3$  toxicities, except those that have not been maximally treated (eg, nausea, vomiting, diarrhea).*
  - *Delay by more than 2 weeks in receiving the next scheduled cycle due to persisting toxicities not attributable to disease progression.*

*In addition, clinically important or persistent toxicities that are not included in the above criteria may be considered a DLT following review by the sponsor and the investigators.*

*Grade  $\geq 3$  cytokine release syndrome, infusion reaction, and allergic reaction will not be considered as DLTs but may be a reason for study discontinuation and should be reviewed with the sponsor.*

#### **7.2.2. Vitals**

See Schedule of Activities in the protocol for details.

#### **7.2.3. Laboratory Data**

The laboratory results will be graded according to the NCI CTCAE v4.03 severity grade. For labs for which an NCI CTCAE v4.03 scale does not exist, the frequency of subjects with values below, within, and above the normal ranges will be summarized by dose. Baseline evaluations for laboratory data are those collected:

- Within 28 days prior to Cycle 1/Day 1.
- Closest but prior to Cycle 1/Day 1 if there is more than one baseline evaluation.

#### **7.2.4. Adverse Events**

*Assessment of adverse events will include the type, incidence, severity (graded by the National Cancer Institute Common Terminology Criteria for Adverse Events [NCI CTCAE] version 4.03) timing, seriousness, and relatedness.*

All AEs will be coded by system organ class (SOC) and preferred term using Medical Dictionary for Regulatory Activities (MedDRA). The severity of all AEs will be graded by the investigator using NCI CTCAE version 4.03 whenever possible. For other AEs without specific CTC definitions, results are identified according to CTCAE “other” categories. Adverse events will be assigned to the appropriate cycle based on Day 1 of each cycle.

#### **Treatment Emergent Adverse Events**

- All deaths from start of treatment until 28 days after the final dose.

- All treatment related SAEs.
- All unrelated SAEs from treatment start until 28 days after final dose of treatment.
- All non-fatal AEs occurring after treatment start up until 28 days after final dose of treatment or until start of new anti-cancer treatment, whichever is first.
- Disease progression is not considered a treatment emergent adverse event unless the subject dies of disease prior to 28 days after discontinuation of treatment.
- Events that are continuations of baseline abnormalities are considered treatment emergent adverse events only if there is an increase in grade over baseline.

